## **Appendix 2**

### **Adverse Events: Definitions and Procedures for Evaluating, Follow-up and Reporting**

#### **1. DEFINITION OF ADVERSE EVENTS**

According to the E2A ICH guideline for Good Clinical Practice, an **adverse event** is any untoward medical occurrence in a patient or clinical investigation participant administered a pharmaceutical product and which does not necessarily have to have a causal relationship with this treatment.

An adverse event can therefore be:

- Any unfavorable and unintended sign (including an abnormal laboratory finding), symptom, or disease temporally associated with the use of a medicinal product, whether or not considered related to the medicinal product.

#### **Events Meeting the AE Definition:**

- Any deterioration in a laboratory value (hematology, clinical chemistry, or urinalysis) or other clinical test (e.g., ECG, X-ray) that is associated with symptoms or leads to a change in study treatment or concomitant treatment or discontinuation from study treatment.
- Exacerbation of a chronic or intermittent pre-existing condition, including either an increase in frequency and/or intensity of the condition.
- New conditions detected or diagnosed after study treatment administration even though it may have been present before the start of the study.
- Adverse events that are related to a protocol-mandated intervention, including those that occur prior to assignment of study treatment (e.g., screening invasive procedures such as biopsies).
- "Lack of efficacy" or "failure of expected pharmacological action" per se will not be reported as an AE or SAE unless the progression is unexpectedly accelerated and not in line with the natural history of the disease. If the "Lack of efficacy" would not require safety reporting such instances will be captured in the efficacy assessments. However, the signs, symptoms, and/or clinical sequelae resulting from lack of efficacy will be reported as AE or SAE if they fulfill the definition of an AE or SAE.

#### **Events NOT Meeting the AE Definition:**

- Any clinically significant abnormal laboratory findings or other abnormal safety assessments which are associated with the underlying disease, unless judged by the Investigator to be more severe than expected for the participant's condition.
- The disease/disorder being studied or expected progression, signs, or symptoms of the disease/disorder being studied, unless more severe than expected for the participant's condition.

- Medical or surgical procedure (e.g., endoscopy, appendectomy): the condition that leads to the procedure is an AE.
- Situations where an untoward medical occurrence did not occur (social and/or convenience admission to a hospital).
- Anticipated day-to-day fluctuations of pre-existing disease(s) or condition(s) present or detected at the start of the study that do not worsen.

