- Procedure-Related Risks

The procedures performed are flexible sigmoidoscopy (or possible colonoscopy at screening) with mucosal biopsies from the sigmoid colon, SC injections and blood draws. The risks associated with flexible sigmoidoscopy or colonoscopy with biopsies include bleeding, infection, and perforation of the intestine. SC injections may produce a local inflammatory reaction, which can range from a slight irritation to infection or possible necrosis. The risks associated with blood draws include hematoma, and rarely injury to neurovascular structures.

- Risks Related to Concomitant Medications

Risks of Corticosteroid and RO7049665 Adjunctive Therapy

Long-term use of corticosteroids is associated with pleiotropic effects, which are well described ([Ford et al. 2011](#)). An increased susceptibility to infection is a known side effect. Addition of RO7049665 could theoretically further increase the risk of infection. Current standard of care includes the addition of other immune-modulating therapeutics on a background of corticosteroid therapy, with the goal of therapy being to discontinue corticosteroids. Patients in this study may continue on a maximum dose of prednisone that will not exceed 20 mg/day for a maximum of 12 weeks of therapy. Corticosteroid dose could be decreased in response to steroid-associated side effects to minimize the toxicity of chronic

therapy with corticosteroids. Addition of RO7049665 to background corticosteroid therapy will follow standard of care practices since rapid discontinuation of corticosteroids is not acceptable due to the risk of adrenal insufficiency.

- **Exacerbation of UC**

Patients with UC have a significant inflammatory burden from the ongoing disease. There is a potential risk of activating and expanding CD25+ Teff cells with RO7049665, or development of excessive IL-2 effects as described above.

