**Table 4 Objectives and Endpoints**

Objectives	Endpoints
Primary	

To evaluate the safety and tolerability of repeat dosing of subcutaneous (SC) injections of RO7049665 in participants with active ulcerative colitis (UC).

	

Incidence of dose-limiting or intolerable treatment-related adverse events (AEs).

Incidence, severity, and causal relationship of treatment-emergent AEs.

Incidence of abnormal laboratory findings.

Incidence of abnormal vital signs and electrocardiogram (ECG) parameters.

Secondary	

To investigate the multiple-dose pharmacokinetics of RO7049665.

	

Pharmacokinetic parameters of RO7049665

To investigate the effects of multiple doses of RO7049665 on changes in endoscopic appearance of the mucosa of the sigmoid colon.

	

Change from baseline in the Endoscopy Subscore of the Mayo Clinic Score (MCS-ES) at Day 29 and Day 57.

Change from baseline in the Ulcerative Colitis Endoscopic Index of Severity (UCEIS) at Day 29 and Day 57.

To investigate the effects of multiple doses of RO7049665 on changes in histologic appearance of mucosa in biopsies from the sigmoid colon.

	

Change from baseline to Day 29 and Day 57 in histology score of sigmoid colon biopsies (Geboes Score [GS], Robarts Histology Index [RHI], or Nancy Histology Index [NHI]).

To investigate the effects of multiple doses of RO7049665 on changes in disease activity.

	

Change from baseline in the Mayo Clinic Score (MCS) at Day 29 and Day 57.

To evaluate the immunogenicity of RO7049665.

	

Incidence of anti-drug antibodies (ADAs).

To investigate the effects of multiple doses of RO7049665 on immune cells in the periphery and in mucosal biopsies of the sigmoid colon.

	

Quantitative changes in WBCs (<math>T_{reg}</math>, <math>T_{eff}</math>, natural killer [NK] cells, B cells and eosinophils).

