#### **4.1.4 Individual Participant Stopping Criteria**

Dosing will be stopped in a given individual participant if, compared with baseline, one of the following circumstances occurs:

- *A second systemic IRR or hypersensitivity AE of any grade occurs (see Sections 4.1.5 and 8.3.8).*
- Grade 3 or greater severe AE or SAE considered related to study drug, including but not limited to:
  - *IRR/ hypersensitivity reaction which is considered related to study drug and believed to pose an unacceptable risk if the dose is repeated.*
  - *CLS including severe, clinically significant respiratory distress syndrome, edema, effusions, or decrease in blood pressure*
- Disease exacerbation requiring escalation of baseline treatment or other treatment strategies (pharmacological or surgical) signifying study treatment failure (See Section 7).
- Development of neutralizing antibodies to recombinant human IL-2 (also see study stopping criteria Section 4.1.3).
- Other findings that, at the discretion of the Investigator, indicate that dosing should be stopped.

Study closure information is provided in [Appendix 1](#).

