### **8.3.7 Disease-Related Events and/or Disease-Related Outcomes Not Qualifying as AEs or SAEs**

Not applicable for the participants in this study.

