## 2. **DEFINITION OF SERIOUS ADVERSE EVENTS**

If an event is not an AE per definition above, then it cannot be a serious adverse event (SAE) even if serious conditions are met (e.g., hospitalization for signs/symptoms of the disease under study, death due to progression of disease).

A serious adverse event is defined as any untoward medical occurrence that at any dose:

- **Results in death.**
- **Is life-threatening.**

The term "life-threatening" in the definition of "serious" refers to an event in which the participant was at risk of death at the time of the event; it does not refer to an event which hypothetically might have caused death if it was more severe.

- **Requires inpatient hospitalization or prolongation of existing hospitalization** (see [Appendix 3](#)).

In general, hospitalization signifies that the participant has been detained (usually involving at least an overnight stay) at the hospital or emergency ward for observation and/or treatment that would not have been appropriate in the physician's office or outpatient setting. Complications that occur during hospitalization are AEs. If a complication prolongs hospitalization or fulfills any other serious criteria, the event is serious. When in doubt as to whether "hospitalization" occurred or was necessary, the AE should be considered serious.

Hospitalization for elective treatment of a pre-existing condition that did not worsen from baseline is not considered an AE.

- **Results in persistent or significant disability/incapacity**

Disability means substantial disruption of the participant's ability to conduct normal life functions.

This definition is not intended to include experiences of relatively minor medical significance such as uncomplicated headache, nausea, vomiting, diarrhea, influenza, and accidental trauma (e.g., sprained ankle) which may interfere with or prevent everyday life functions but do not constitute a substantial disruption.

- **Is a congenital anomaly/birth defect.**

- **Other significant events:**

Medical or scientific judgment should be exercised in deciding whether SAE reporting is appropriate in other situations such as important medical events that may not be immediately life-threatening or result in death or hospitalization but may jeopardize the participant or may require medical or surgical intervention to prevent one of the other outcomes listed in the above definition. These events should usually be considered serious.

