**9. LACK OF EFFICACY OR WORSENING OF ULCERATIVE COLITIS**

Medical occurrences or symptoms of deterioration that are anticipated as part of ulcerative colitis should be recorded as an adverse event if judged by the Investigator to have unexpectedly worsened in severity or frequency or changed in nature at any time during the study. When recording an unanticipated worsening of ulcerative colitis on the Adverse Event eCRF, it is important to convey the concept that the condition has changed by including applicable descriptors (e.g., “accelerated ulcerative colitis”).

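### Section 8.3.7 and the adverse event appendices disagree on UC worsening, so a flare judged expected can be left out of the AE and SAE tables, and no planned safety table recovers it

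*Combined protocol and SAP*

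**What the plan says.** Four parts of the protocol bear on how a UC flare is recorded.

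- **Risk.** Section 2.3 lists "Exacerbation of UC" among the potential risks, through activation and expansion of effector T cells, and judges that risk minimal. Section 4.2.2 gives the need to tell disease complications from drug signals as a reason for the placebo arm.
- **Clinical criteria.** Section 8.2.8 defines exacerbation as a partial Mayo rise of more than 2 points from baseline over two consecutive visits. Section 4.1.4 stops dosing for "Disease exacerbation requiring escalation of baseline treatment or other treatment strategies (pharmacological or surgical) signifying study treatment failure".
- **Recording rules.** Appendix 2 Section 1 counts as an AE "Exacerbation of a chronic or intermittent pre-existing condition, including either an increase in frequency and/or intensity of the condition". The same section excludes "The disease/disorder being studied or expected progression, signs, or symptoms of the disease/disorder being studied, unless more severe than expected". Appendix 3 Section 9 says that anticipated symptoms of deterioration in UC "should be recorded as an adverse event if judged by the Investigator to have unexpectedly worsened in severity or frequency or changed in nature". Appendix 2 Section 2 adds that if an event is not an AE "then it cannot be a serious adverse event (SAE) even if serious conditions are met (e.g., hospitalization for signs/symptoms of the disease under study". Section 8.3.7, headed as covering disease-related events that do not qualify as AEs or SAEs, reads "Not applicable for the participants in this study".
- **Endpoint.** A primary endpoint in Table 4 is "Incidence, severity, and causal relationship of treatment-emergent AEs".

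**The concern.** Section 8.3.7 tells a site that this study has no class of disease-related events exempt from AE reporting. The two appendices create such a class and leave entry to it to the Investigator's view of what was expected. Neither Section 8.2.8 nor Section 4.1.4 says that a flare meeting its criterion must be recorded as an AE.

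Two sites could therefore handle the same flare differently, and both could cite the protocol. The primary safety tables would then under-count, by an unknown and site-dependent amount, a risk that the protocol itself names. The filter acts before the data reach the treatment-group comparison that the placebo arm is meant to support. Section 4.3 adds some weight: it predicts a trend to higher CD4+ effector T cells, about 1.5-fold after the fourth dose, at 15 mg.

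**Working it through.** **1. The rules side by side.** Take a participant whose partial Mayo score rises by more than 2 points over two consecutive visits, whose UC therapy is escalated, and whose dosing is stopped.

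| Rule | Is the flare an AE? |
|---|---|
| Appendix 2 Section 1, events meeting the definition | Yes; no expectedness test |
| Appendix 3 Section 8 (condition present at screening that worsens) | Yes on its literal terms; UC is not carved out |
| Section 8.3.7 | No exempt class exists |
| Appendix 2 Section 1, events not meeting the definition | No, unless more severe than expected for that participant |
| Appendix 3 Section 9 | Only if judged unexpectedly worse or changed in nature |
| Appendix 2 Section 2 | If not an AE, then not an SAE, even with hospitalisation |

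Appendix 2 Section 1 also says that signs and sequelae of lack of efficacy are reported if they meet the AE definition. That does not settle the matter, because the exclusion list takes expected signs and symptoms out of the definition.

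**2. Would another planned output show the flare by arm?**

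- Table 7 has rows for AEs, laboratory tests, vital signs, ECG, concomitant medications and other items (physical examination, safety biomarkers, ADA). None covers partial Mayo scores or exacerbation.
- Section 9.3.4 analyses scores at Day 57, with Day 29 described. Its composite pools early treatment discontinuation for any reason with non-response.
- Section 9.5 summarises and lists discontinuations, but plans no count of flares by treatment group.

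**3. Size.** Section 9.2 gives the chance of at least one event with a true rate of 20%. With n participants, rate p and every event recorded, this is 1 − (1 − p)^n:

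- n = 8: 1 − 0.8^8 = 1 − 0.168 = 0.832 (stated 83%).
- n = 4: 1 − 0.8^4 = 1 − 0.410 = 0.590 (stated 59%).

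Both reproduce. If only a share c of flares is recorded, independently of one another, p becomes p × c. Both p and c are assumptions here.

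| Share recorded, c | n = 8, p = 10% | n = 8, p = 20% | n = 8, p = 30% | n = 4, p = 20% |
|---|---|---|---|---|
| 1 | 0.570 | 0.832 | 0.942 | 0.590 |
| 0.75 | 0.464 | 0.728 | 0.870 | 0.478 |
| 0.5 | 0.337 | 0.570 | 0.728 | 0.344 |
| 0.25 | 0.183 | 0.337 | 0.464 | 0.185 |
| 0 | 0 | 0 | 0 | 0 |

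For example, at c = 0.5 and p = 20%, 1 − 0.9^8 = 1 − 0.430 = 0.570.

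**The case against.** The sponsor can answer much of this.

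- **The specific rule governs.** Section 8.3 lists pre-existing conditions and worsening of the condition under study as separate topics, and Appendix 3 gives each its own section. On that reading Appendix 3 Section 9 governs UC, and the clash with the general exacerbation rule largely goes away. This stands. It does not remove the clash with Section 8.3.7, and it leaves recording to site judgement.
- **The exemption is conditional.** It tests severity against the participant's own condition. A sustained flare needing escalated therapy could well be judged worse than expected, and Appendix 2 says that the condition leading to a surgical procedure is an AE. This stands too: such a flare can be recorded, but nothing requires it.
- **The Sponsor hears anyway.** Section 4.1.5 requires immediate contact for any event meeting a Section 4.1.4 criterion, so it would be wrong to infer that a dose-stopping flare goes unreported. That contact is not an AE record, though, and does not feed the tables. Nor does a dosing stop apply to a flare arising after the last dose on Day 43, with follow-up to Day 99.
- **Deaths.** A reader might infer from Appendix 2 Section 2 that a death from UC escapes. Appendix 3 Section 7 requires every death in the reporting period to be recorded and reported, whatever its cause.
- **The dose-level stopping rule.** A reader might infer that the Section 4.1.3 rule is disabled. It counts only Grade 3 or higher drug-related AEs of the same type. A flare judged drug-related is hard to call expected progression, and a discretionary criterion for other findings remains.
- **The data exist.** Partial Mayo scores, concomitant medications and discontinuation reasons are collected in all arms. A comparison of flares is therefore possible; it is not planned.

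**Conclusion.** The contradiction between Section 8.3.7 and the two appendices is real and should be reconciled. As written, site judgement of expectedness can keep a named potential risk out of the primary safety tables, and no planned table recovers it.

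The consequence is possible under-counting. The documents do not support saying that flares are never AEs, that they go unseen, or that arms cannot be compared. No stated figure is wrong: the 83% and 59% in Section 9.2 hold for events that are all recorded. If half of flares were recorded at an assumed 20% rate, they would fall to 57% and 34%. With 8 treated, the same halving gives 57% to 34% at an assumed 10% rate and 94% to 73% at 30%. The zero row is only a bound, since it needs every site to exempt every flare. Section 9.2 uses 20% as a generic AE rate, not a flare rate, and no document gives the share recorded.

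**What to change.** 1. **One recording rule.** Reconcile Section 8.3.7, Appendix 2 Sections 1 and 2, and Appendix 3 Section 9 so that a single rule for recording UC worsening applies in all arms. Tie it to facts the protocol already defines or records: the Section 8.2.8 criterion is met, dosing is stopped for disease exacerbation under Section 4.1.4, or the participant is hospitalised. Assess such events for severity, causality and seriousness like any other AE, instead of screening them first for expectedness.
2. **One added safety table.** By treatment group, count the participants who meet the Section 8.2.8 criterion or are stopped for disease exacerbation under Section 4.1.4, regardless of AE status. State which pre-dose partial Mayo score is the baseline, and check that the eCRF discontinuation reasons identify disease exacerbation.

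This changes recording and tabulation only; no dosing, treatment or stopping rule is altered. The cost is protocol wording, an eCRF guideline note, one table, and somewhat higher AE and SAE counts in every arm from natural disease activity. The second step uses data already collected and is worth doing even if the sponsor keeps an expectedness test.

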## 2. **DEFINITION OF SERIOUS ADVERSE EVENTS**

If an event is not an AE per definition above, then it cannot be a serious adverse event (SAE) even if serious conditions are met (e.g., hospitalization for signs/symptoms of the disease under study, death due to progression of disease).

A serious adverse event is defined as any untoward medical occurrence that at any dose:

- **Results in death.**
- **Is life-threatening.**

The term "life-threatening" in the definition of "serious" refers to an event in which the participant was at risk of death at the time of the event; it does not refer to an event which hypothetically might have caused death if it was more severe.

- **Requires inpatient hospitalization or prolongation of existing hospitalization** (see [Appendix 3](#)).

In general, hospitalization signifies that the participant has been detained (usually involving at least an overnight stay) at the hospital or emergency ward for observation and/or treatment that would not have been appropriate in the physician's office or outpatient setting. Complications that occur during hospitalization are AEs. If a complication prolongs hospitalization or fulfills any other serious criteria, the event is serious. When in doubt as to whether "hospitalization" occurred or was necessary, the AE should be considered serious.

Hospitalization for elective treatment of a pre-existing condition that did not worsen from baseline is not considered an AE.

- **Results in persistent or significant disability/incapacity**

Disability means substantial disruption of the participant's ability to conduct normal life functions.

This definition is not intended to include experiences of relatively minor medical significance such as uncomplicated headache, nausea, vomiting, diarrhea, influenza, and accidental trauma (e.g., sprained ankle) which may interfere with or prevent everyday life functions but do not constitute a substantial disruption.

- **Is a congenital anomaly/birth defect.**

- **Other significant events:**

Medical or scientific judgment should be exercised in deciding whether SAE reporting is appropriate in other situations such as important medical events that may not be immediately life-threatening or result in death or hospitalization but may jeopardize the participant or may require medical or surgical intervention to prevent one of the other outcomes listed in the above definition. These events should usually be considered serious.

Examples of such events include invasive or malignant cancers, intensive treatment in an emergency room or at home for allergic bronchospasm, blood dyscrasias or convulsions that do not result in hospitalization, or development of drug dependency or drug abuse.

For **protocol-specific significant events**, see Sections [4.1.4](#) and [7.1](#) for consideration.

### **3. RECORDING OF ADVERSE EVENT AND/OR SERIOUS ADVERSE EVENT**

When an AE/SAE occurs, it is the responsibility of the Investigator to review all documentation (e.g., hospital progress notes, laboratory reports, and diagnostics reports) related to the event.

The Investigator will then record all relevant AE/SAE information in the CRF.

It is **not** acceptable for the Investigator to send photocopies of the participant's medical records to Medical Monitor in lieu of completion of the eCRF.

There may be instances when copies of medical records for certain cases are requested by the Sponsor. In this case, all participant identifiers, with the exception of the participant number, will be redacted on the copies of the medical records before submission to the Sponsor.

The Investigator will attempt to establish a diagnosis of the event based on signs, symptoms, and/or other clinical information. Whenever possible, the diagnosis (not the individual signs/symptoms) will be documented as the AE/SAE.

